12.4 Technical complaints and technical complaint samples

12.4.1 Reporting of technical complaints

All technical complaints on any of the following products:

- Turoctocog alfa 2000 IU/vial
- Isotonic Sodium Chloride 0.9% for injection in prefilled syringes
- Novo Nordisk trial injection kit

which occur from the time of first usage of the product until the time of the last usage of the product, must be collected and reported to Customer Complaint Center, Novo Nordisk.

Contact details (fax, e-mail and address) are provided in Attachment I to the protocol.

The investigator must assess whether the technical complaint is related to any AEs or SAEs. Technical complaints must be reported on a separate technical complaint form:

- One technical complaint form must be completed for each affected DUN
- If DUN is not available, a technical complaint form for each batch, code or lot number must be completed

The investigator must complete the technical complaint form in the eCRF within the following timelines of the trial site obtaining knowledge of the technical complaint:

- Technical complaint assessed as related to an SAE within 24 hours
- All other technical complaints within 5 calendar days

If the eCRF is unavailable or when reporting a technical complaint that is not patient related, the information must be provided on a paper form by fax, e-mail or courier to Customer Complaint Center, Novo Nordisk, within the same timelines as stated above. When the eCRF becomes available again, the investigator must enter the information on the technical complaint form in the eCRF.

12.4.2 Collection, storage and shipment of technical complaint samples

The investigator must collect the technical complaint sample and notify the monitor **within 5 calendar days** of obtaining the sample at trial site. The monitor must coordinate the shipment to Customer Complaint Center, Novo Nordisk (the address is provided in Attachment I) and ensure that the sample is sent as soon as possible. A copy of the technical complaint form must be included in the shipment of the sample. If several samples are returned in one shipment, the individual sample and the corresponding technical complaint form must be clearly separated.

Protocol		Date:	13 June 2017	Novo Nordisk
Trial ID: NN7008-4304	CONFIDENTIAL	Version:	2.0	
UTN:U1111-1179-5950	CONFIDENTIAL	Status:	Final	
EudraCT no.:2017-002281-46		Page:	56 of 81	

The investigator must ensure that the technical complaint sample contains the batch, code or lot number and, if available, the DUN. All parts of the DUN must be returned.

If the technical complaint sample is unobtainable, the investigator must specify on the technical complaint form why it is unobtainable.

Storage of the technical complaint sample must be done in accordance with the conditions prescribed for the product.

12.5 Precautions and/or overdose

As with any protein injected i.v, hypersensitivity reactions may occur. This might include rash, pruritus, fever, nausea, headache, and vomiting; also changes in BP may occur.

If an overdose is suspected, further turoctocog alfa administration must be stopped and the patient should receive treatment as appropriate according to the hospital practice and guidelines.

12.6 Committees related to safety

12.6.1 Novo Nordisk safety committee

Novo Nordisk will constitute an internal turoctocog alfa safety committee to perform ongoing safety surveillance. The turoctocog alfa safety committee works according to written guidelines and will meet regularly to discuss and evaluate the overall safety of turoctocog alfa.

The Novo Nordisk safety committee can take action with regard to patient safety for the trial based upon observations of the overall safety information for turoctocog alfa.

 Protocol
 Date:
 13 June 2017
 Novo Nordisk

 Trial ID: NN7008-4304
 Version:
 2.0
 Status:
 Final

Page:

57 of 81

13 Case report forms

EudraCT no.:2017-002281-46

Novo Nordisk will provide a system for the electronic case report forms (eCRF). This system and support services to the system will be provided by an external supplier.

Ensure that all relevant questions are answered, and that no empty data field exists. If a test or an assessment has not been done and will not be available, or if the question is irrelevant (e.g. is not applicable), indicate this according to the data entry instructions. The following will be provided as paper CRFs to be used when access to the eCRF is revoked or if the eCRF is unavailable:

- AE forms
- Safety information forms
- Technical complaint forms

On the paper CRF forms print legibly, using a ballpoint pen. Ensure that all questions are answered, and that no empty data blocks exist. Ensure that no information is recorded outside the data blocks. If a test/assessment has not been done and will not be available, indicate this by writing "ND" (not done) in the appropriate answer field in the CRF. If the question is irrelevant (e.g. is not applicable) indicate this by writing "NA" (not applicable) in the appropriate answer field. Further guidance can be obtained from the instructions in the CRF.

The investigator must ensure that all information is consistent with the source documentation. By electronically signing the case book in the eCRF, the investigator confirms that the information in the eCRF and related forms is complete and correct.

13.1 Corrections to case report forms

13.1.1 Corrections to paper CRFs

Corrections to the data in CRFs may only be made by drawing a straight line through the incorrect data and then writing the correct entry next to the data that was crossed out. Each correction must be initialled, dated and explained (if necessary). The date format must be DD-MMM-YY (e.g.01-Jan-13).

If corrections are made by the investigator's delegated staff after the date of the investigator's signature on the casebook in eCRF, the casebook must be signed again.

13.1.2 Corrections to eCRFs

Corrections to the eCRF data may be made by the investigator or the investigator's delegated staff. An audit trail will be maintained in the eCRF application containing as a minimum: the old and the new data, identification of the person entering the data, date and time of the entry and reason for the correction

Protocol		Date:	13 June 2017	Novo Nordisk
Trial ID: NN7008-4304	CONFIDENTIAL	Version:	2.0	
UTN:U1111-1179-5950	CONFIDENTIAL	Status:	Final	
EudraCT no :2017-002281-46		Page:	58 of 81	

If corrections are made by the investigator's delegated staff after the date the investigator has signed the case book, the case book must be signed and dated again by the investigator.

13.2 Case report form flow

The investigator must ensure that data is recorded in the eCRF as soon as possible, preferably within 5 days after the visit. Once data has been entered, it will be available to Novo Nordisk for data verification and validation purposes.

Site specific eCRF data (in an electronic readable format) will be provided to the trial site before access to the eCRF is revoked. This data must be retained at the trial site.

The paper CRFs will be supplied as paper-set including two different coloured copies. The CRA (clinical research associate) will collect the original (top page) during the monitoring visits after source data verification (SDV) has been performed and send it to data management. One copy (bottom page) of the CRF will be retained at the site. The CRA will keep the middle copy of the CRFs.

Central laboratory results will be transferred electronically to Novo Nordisk and will also be provided to the investigator.

13.3 Diary

Two set of paper diaries will be provided by Novo Nordisk A/S and will be handed to the patients at visit 1 (see section 8.6.2). The completed diary will be returned by the patient at every visit to the site and at the end of the trial. The data from the diaries will be checked by the investigator or site staff and reported into the eCRF. Corrections to this data may be made by investigator or the investigator's delegated staff after a discussion with patient and the same should be documented in the patient's medical or source records.

14 Monitoring procedures

Monitoring will be conducted using risk based approach including risk assessment, monitoring plans centralised monitoring and visits to trial sites. During the course of the trial, the monitor will visit the trial site to ensure that the protocol is adhered to, and that all issues have been recorded, to perform source data verification and to monitor drug accountability. The first monitoring visit will be performed as soon as possible after FPFV at the specific site and no later than 4 weeks after. The monitoring visit intervals will depend on the outcome of the centralised monitoring of the eCRFs (remote assessment of data by Novo Nordisk), the trial site's recruitment rate and the compliance of the trial site to the protocol and GCP¹, but will not exceed 12 weeks. This is though not a requirement after LPLV at the specific site.

The monitor must be given direct access to source documents (original documents, data and records). Direct access includes permission to examine, analyse, verify and reproduce any record(s)

Protocol Trial ID: NN7008-4304 UTN:U1111-1179-5950	CONFIDENTIAL	Date: Version: Status:	13 June 2017 2.0 Final	Novo Nordisk
EudraCT no.:2017-002281-46		Page:	59 of 81	

and report(s) that are important to the evaluation of the trial. If the electronic medical record does not have a visible audit trail, the investigator must provide the monitor with signed and dated printouts. In addition the relevant trial site staff should be available for discussions at monitoring visits and between monitoring visits (e.g. by telephone).

All data must be verifiable in source documentation other than the eCRF, except for the data in the diary.

For all data recorded the source document must be defined in a source document agreement at each trial site. There must only be one source defined at any time for any data element.

The investigator must make a reasonable effort to obtain the following medical history from external sources e.g. primary physician and other hospitals/departments if not accessible in the medical records. The effort to obtain this information must be documented in the medical records:

- Any positive inhibitor history
- Known or suspected hypersensitivity to trial product(s) or other FVIII products
- Congenital or acquired coagulation disorders other than haemophilia A
- Any disorder which, in the opinion of investigator, might jeopardise patient's safety or compliance with the protocol
- Mental incapacity
- Haemophilia treatment and bleeding episode history

All the above elements in the patient's medical history are required for evaluating different exclusion criteria in this trial; see section $\underline{6.3}$, except the last point which is not an exclusion criterion.

The following medical history the trial site do not need to require from other external sources e.g. primary physician and other hospitals/departments if not accessible in the medical records as these can be tested in this trial:

- Diagnose of FVIII severity
- HIV, CD4+ T cell status and viral load
- Hepatitis B and C

All the above elements in the patient's medical history are required for evaluating different inclusion and exclusion criteria, see section $\underline{6}$, except the hepatitis B and C test.

It must be evaluated carefully what data is source data. The earliest practically retainable record should be considered as the location of the source data and therefore the source document, for instance if any electronic instruments are used for measuring vital signs the printout from these

Protocol		Date:	13 June 2017	Novo Nordisk
Trial ID: NN7008-4304	CONFIDENTIAL	Version:	2.0	
UTN:U1111-1179-5950		Status:	Final	
EudraCT no.:2017-002281-46		Page:	60 of 81	

instruments should be considered as the source. The laboratory reports sent to the site should also be considered the source. The data entered directly into the diary are also considered as source.

Source data generated by the trial site can be corrected by another person than the person entering the source data if accepted by local regulations; any correction must be explained, signed and dated by the person making the correction.

If paper CRF are used, each copy of the paper CRF are considered to be source and this allows that the top page of the paper CRF to be removed from the trial site and sent to data management. Data is entered directly into the diary and thus the diary is considered to be the source.

The monitor will check that the eCRFs, paper CRFs and the diary are completed and that paper CRFs are collected.

The monitor will check eCRF pages and other trial-related forms containing data from screening failures. The following data will be source data verified for screening failures:

- Date of informed consent
- Violated Inclusion and exclusion criteria
- Screen failure reason
- Date patient left the trial
- Data relating to AE/SAEs if applicable
- Demography
- Date of visit

Monitors must review the patient's medical records and other source data (e.g. the diaries) to ensure consistency and/or identify omissions compared to the eCRF. If discrepancies are found, the investigator must be questioned about these.

A follow-up letter (paper or electronic) will be sent to the investigator following each monitoring visit addressing any action to be taken.

See section 9.4 how drug accountability must be performed.

13 June 2017 | Novo Nordisk Protocol Date: Trial ID: NN7008-4304 Version: CONFIDENTIAL UTN:U1111-1179-5950 Status: EudraCT no.:2017-002281-46 Page: 61 of 81

Data management

Data management is the responsibility of Novo Nordisk. Appropriate measures, including encryption of data files containing person identifiable data, will be used to ensure confidentiality of patient data, when they are transmitted over open networks.

Final

Data from central laboratories will be transferred electronically. In cases where data is transferred via non-secure electronic networks, data will be encrypted during transfer. The central will provide all laboratory reports to the investigator for storage at the trial site.

The patient and any biological material obtained from the patient will be identified by patient number and trial identification number. Appropriate measures such as encryption or leaving out certain identifiers will be enforced to protect the identity of patients in all presentations and publications as required by local, regional and national requirements.

Computerised systems

Novo Nordisk will capture and process clinical data using computerised systems that are described in Novo Nordisk Standard Operating Procedures and IT architecture documentation. The use and control of these systems are documented.

Investigators working on the trial may use their own electronic systems to capture source data.

Statistical considerations

If necessary, a statistical analysis plan (SAP) may be written in addition to the protocol, including a more technical and detailed elaboration of the statistical analyses. The SAP will be finalised before database lock.

No formal statistical testing will be performed. When confidence intervals are provided they will be two-sided 95% intervals.

17.1 Sample size calculation

Sample size is based on Indian Health Authorities (HA) requirements. Indian HA has mandated Novo Nordisk to perform a trial with 50 patients (completers). Based on Hanley's formula $\frac{31}{2}$ "the rule-of-three" we know that with approximately 95% power we will observe at least one patient with FVIII inhibitor (≥ 0.6 BU) if the incidence rate is as low as 6%. The same holds for any other type of adverse events.

17.2 **Definition of analysis sets**

All main descriptions and analyses of efficacy will be based on the Full Analysis Set, as defined in ICH E9 Guidelines (Statistical Principles for Clinical Trials). ³² The Full Analysis Set includes all

Protocol		Date:	13 June 2017	Novo Nordisk
Trial ID: NN7008-4304	CONFIDENTIAL	Version:	2.0	
UTN:U1111-1179-5950		Status:	Final	
EudraCT no.:2017-002281-46		Page:	62 of 81	

dosed patients with data after dosing. Only in exceptional cases will patients be excluded from the full analysis set. The patients to be excluded and the reasons for their exclusion must be documented and signed by those responsible before database lock. Only in exceptional cases data points will be excluded from analysis based on the full analysis set. The observations to be excluded from such analysis and the reasons for their exclusion must be documented and signed by those responsible before database lock. The patients and observations excluded from analysis sets or any analyses, and the reason for this, will be described in the clinical trial report.

The Safety Analysis Set will be identical to the full analysis set. The analyses of the safety endpoints will be based on the Safety Analysis Set. The observation period for safety analysis will be the on-treatment period with a post treatment window until the follow-up visit to capture all treatment emergent events. The observation period is therefore from fist treatment with trial drug (visit 2) until the follow-up visit.

No formal Per-Protocol analysis is planned. However, the sensibility of the results with respect to single patient's data may be investigated by performing additional analyses on subsets of data.

Missing inhibitor test will not be counted as a positive result. This is based on the plausible assumption that in case of any clinical signs of inhibitor development inhibitor testing will be performed in practice, so missing test is unlikely to indicate positive inhibitor.

In general the statistical analysis will be based on the available data, unless otherwise explicitly stated below.

17.3 Primary endpoint

Occurrence of confirmed FVIII inhibitors (≥0.6 BU) during 8 weeks of treatment.

A patient is said to have confirmed FVIII inhibitor when two consecutive tests are positive. In case of confirmation the inhibitor is considered to have been present from the first of the two tests. The estimand for the primary endpoint is an effectiveness estimand among all exposed subject. The incidence rate of inhibitors will be calculated and a 1-sided 97.5% upper confidence limit will be provided based on an exact calculation for a binomial distribution. For the calculation of the incidence rate the numerator will include number of all patients with confirmed inhibitors anytime after baseline visit while the denominator will include the number of patients in the safety analysis set.

Furthermore, listings will be provided displaying inhibitor status including pertinent clinical information such as gene mutation.

Protocol Trial ID: NN7008-4304 UTN:U1111-1179-5950 EudraCT no.:2017-002281-46

CONFIDENTIAL

Date: Version: Status: Page:

13 June 2017 | Novo Nordisk Final 63 of 81

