4.2 Endpoint(s)

4.2.1 Primary endpoint

• Occurrence of confirmed FVIII inhibitor development (≥ 0.6 BU) during 8 weeks of treatment

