5.4 Treatment after discontinuation of trial product

When discontinuing trial products, either at the scheduled end of trial visit or if trial product is discontinued prematurely, the patient should be switched to a suitable marketed product at the discretion of the investigator.

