8.1.6 Follow up visit

Patients withdrawn, after visit 2, due to inhibitors must attend a follow up visit in order to evaluate the patient's inhibitor status. This visit should be performed within 4 weeks after end of trial visit with a visit window of \pm 3 days.

Patients who have completed the trial must attend a follow up visit in order to assess any possible AEs. Patients, who have completed the trial, must attend 12 weeks after visit 2, with a window of ± 3 days.

The assessments to be performed at this visit are listed in section 2.

Key reminders:

• Ask if the patient has experiences any AEs since last visit

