8.4.2 Antibodies

8.4.2.1 FVIII inhibitors

FVIII inhibitors will be measured at visit 1 and end of trial visit. If there is any suspicion of FVIII inhibitor development, FVIII inhibitors must be measured at an unscheduled visit. At visit 1, the inhibitor test will be taken for baseline characteristics and must be used for the assessment of exclusion criteria, see section 6.3.

Protocol		Date:	13 June 2017	Novo Nordisk
Trial ID: NN7008-4304	CONFIDENTIAL	Version:	2.0	1
UTN:U1111-1179-5950	CONFIDENTIAL	Status:	Final	1
EudraCT no.:2017-002281-46		Page:	34 of 81	I

Analysis for FVIII inhibitors will be carried out at a central laboratory using the Nijmegen modified Bethesda assay. A positive inhibitor test is defined as ≥ 0.6 Bethesda Unit (BU).

If FVIII inhibitor development is suspected by increased number of bleeding episodes, bleeding episodes difficult to treat and/or peak and trough levels below expected values, a Nijmegen modified Bethesda test must be performed. If the result of the modified Bethesda test is positive, another sample must be collected for a confirmatory Nijmegen modified Bethesda assay at an unscheduled visit preferably within 2 weeks and not later than 4 weeks of the first positive test result from central lab. The diagnosis of inhibitor is made if the patient has been tested positive for inhibitors (≥0.6 BU) at two consecutive tests at central lab.

Blood sampling for FVIII inhibitor test must be performed after a 48 hours washout period since last dosing with any FVIII containing products.

If either tests are below or equal to 5 BU the patient can continue in the trial, unless the patient fulfil withdrawal criteria such as ineffective treatment (see section 6.5).

If the second confirmatory is positive (≥ 0.6 BU) and if one of the two tests is above 5 BU, then the patients must be withdrawn from the trial, see section 6.5. The patient must be followed up at the follow-up visits, see section 8.1.6.

For storage, handling, dispatch, and disposition of samples analysed for FVIII inhibitors at the central laboratory, please refer to detailed guidance in the laboratory manual.

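### The primary endpoint covers inhibitors arising in 8 weeks of treatment, but the 17.3 numerator has a wider window, to about week 12 when read with 17.2

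*Combined protocol and SAP*

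**What the plan says.** **The endpoint.** Section 4.2.1 gives it as "Occurrence of confirmed FVIII inhibitor development (≥ 0.6 BU) during 8 weeks of treatment", and 17.3 repeats it as "Occurrence of confirmed FVIII inhibitors (≥0.6 BU) during 8 weeks of treatment". Section 7 identifies the last assessment of the primary endpoint with the end of trial visit, 8 weeks after baseline.

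**The count.** In the same paragraph of 17.3, "the numerator will include number of all patients with confirmed inhibitors anytime after baseline visit". The rate is taken over everyone in the safety analysis set. A case needs two consecutive positive tests and is dated to the first of them. The estimand is described as an effectiveness estimand among all exposed patients.

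**The safety period.** Section 17.2 sets the window for safety analyses: "The observation period is therefore from fist treatment with trial drug (visit 2) until the follow-up visit". For completers, section 8.1.6 fixes that visit: "Patients, who have completed the trial, must attend 12 weeks after visit 2, with a window of ± 3 days".

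**Testing and treatment around week 8.** Under 8.4.2.1, "FVIII inhibitors will be measured at visit 1 and end of trial visit", with a further test at an unscheduled visit if an inhibitor is suspected. A confirmatory sample may be drawn up to 4 weeks after the first positive result. When trial product ends, section 5.4 says that "the patient should be switched to a suitable marketed product at the discretion of the investigator".

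**The concern.** The endpoint and its numerator describe different sets of patients, and no sentence reconciles them. The 8 weeks looks deliberate: in section 4.2.2 the adverse-reaction and allergic-reaction endpoints are explicitly carried to follow-up at 12 weeks, whereas the primary endpoint is not.

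A discordant patient is possible under the protocol. Completers stop trial product at visit 4 and are followed to week 12. A suspected inhibitor triggers an unscheduled test, and section 8.1.7 sets a start but no end for unscheduled visits. A first positive at week 10 would count under the numerator rule and not under the endpoint.

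The primary result is likely to be zero. If a single case does arise, the choice of window could decide whether the reported incidence is zero or not.

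**Working it through.** **Inputs**
- 60 patients planned to start trial product and 50 to complete (6.1). The safety analysis set is taken as 60, with 50 as a check.
- Exact binomial one-sided 97.5% upper limit (17.3).
- Background inhibitor rate in previously treated patients: 1–3 per 1000 patient-years (3.2).
- Gap between the two windows: week 8 to week 12, or 4/52 year.

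**1. The plan's own figure (17.1).** The chance of at least one case among 50 patients at 6% incidence is 1 − 0.94^50 = 0.9547. This reproduces the stated figure of about 95%. It does not depend on which window is used.

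**2. Which rule counts which case**

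| First positive sample | Endpoint (4.2.1, 17.3) | Numerator (17.3, read with 17.2) |
|---|---|---|
| Weeks 0–8, confirmed by week 8 | counts | counts |
| Week 8 (visit 4), confirmed later | counts, by the dating rule | counts |
| After visit 4, up to follow-up, later confirmed | does not count | counts |

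Only the third row is in dispute. Late confirmation alone creates no conflict, because 17.3 dates the inhibitor to the first test.

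**3. Effect of one such patient**

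For x = 0 the upper limit is 1 − 0.025^(1/n). For x = 1 it is the p that solves (1 − p)^n + n·p·(1 − p)^(n−1) = 0.025.

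| n | x = 0 | x = 1 |
|---|---|---|
| 60 | 0%; limit 1 − 0.025^(1/60) = 5.96% | 1/60 = 1.7%; limit 8.94% |
| 50 | 0%; limit 1 − 0.025^(1/50) = 7.11% | 1/50 = 2.0%; limit 10.65% |

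**4. How likely such a patient is**

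Expected new cases in weeks 8–12 among 60 patients:
- 60 × (4/52) × 0.001 = 0.0046
- 60 × (4/52) × 0.003 = 0.0138

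The chance of at least one is 1 − exp(−0.0046) ≈ 0.5% to 1 − exp(−0.0138) ≈ 1.4%.

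For comparison, weeks 0–8 give 60 × (8/52) × 0.001 = 0.0092 to 60 × (8/52) × 0.003 = 0.0277 expected cases, a 0.9–2.7% chance of at least one.

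**The case against.** The strongest defence is that the time phrase in the numerator was never meant to extend the endpoint. It stands under a line that says 8 weeks. It may only have been meant to admit for-cause samples and confirmatory samples drawn after week 8. That intention is plausible, and such cases do belong in the endpoint. But the dating rule already admits them, and the words as written also admit a first positive after visit 4.

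A second defence is that a wider count is the cautious choice for a safety endpoint and suits an all-exposed estimand. There is something in this. With one scheduled post-baseline test, an inhibitor formed on trial product could be missed at visit 4 and found for cause in week 9, so the later count should be reported. But the estimand says who is counted. It does not lengthen the stated 8 weeks. Ascertainment also differs after visit 4, because no further inhibitor test is scheduled for completers.

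Three stronger readings are tempting, and the documents do not support them:

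- A reader might infer that the numerator has no end. Section 17.2 closes the safety observation period at the follow-up visit.
- A reader might infer that a late case would be another product's inhibitor charged to turoctocog alfa. Section 17.3 says nothing about cases after the switch; that follows only from combining 5.4, 8.1.6, 8.4.2.1 and 17.2. Section 3.2 regards inhibitors as arising without clear association with a change of product. Date alone assigns the case to neither product.
- A reader might infer that the window is free to be chosen once results are known. The counting rule is already written down, and any SAP is to be final before database lock. A case would also be visible in the inhibitor listings (17.3) and as a mandatory serious adverse event (12.1.2). What remains is narrower: two rules stand in one section of an open-label trial whose SAP is optional.

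**Conclusion.** The inconsistency stands in the current text and should be removed. It concerns first positives between the end of the 8-week window and the follow-up visit, about four weeks.

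A single discordant patient would change the primary result from 0/60 to 1/60 and raise the upper limit from 5.96% to 8.94%. That is a conditional effect. The chance of such a patient is about 0.5–1.4%, assuming that 60 patients are followed through week 12, that the protocol's background rate applies evenly over time, and that every case is detected. Detection by clinical suspicion alone would make it smaller; a higher true rate would make it larger. It would be wrong to infer that the headline result is likely to turn on this.

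The sample-size statement is unaffected.

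**What to change.** In 17.3, replace the open-ended time phrase in the numerator so that it counts patients:

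> whose first positive sample was taken after the first dose and within 8 weeks of baseline (including the visit 4 window), whether or not trial product was stopped early, and confirmed by a second consecutive positive sample whenever drawn.

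The limit should be time from baseline, not the end of trial sample. Under 8.1, patients who stop early have their end of trial procedures as soon as possible. A cut-off at that sample would drop, for example, a first positive at week 5 in someone who stopped at week 2, which fits poorly with an all-exposed estimand. It would also be undefined for a patient with no such sample.

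Alongside the primary result:
- Report, as supportive and with the same exact limit, all confirmed inhibitors with a first positive up to the follow-up visit.
- List cases first detected after trial product ended, with the FVIII product in use, without attributing them by date alone.

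The cost is one sentence and one extra summary line, with no new visit, test or patient. The downside is that a rare late inhibitor would appear in the supportive count and not in the primary one.
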